6 SCHEDULE OF ASSESSMENTS

6.1 PK Cohort

Assessment	Screening	Baseline/ Procedure	Day 1	Day 3	Day 7 (±2 d)	Day 14 (±2 d)	Day 21 (±2 d)	Day 30 (±3 d)
Informed consent	X							
Medical/surgical history	X							
CT scan (≤ 30 days prior to enrollment)	X							
Blood sample collection (~11 ml)		X ^a	X ^b	X ^b	X ^b	X ^b		X ^b
24-hour urine collection		X ^c	X ^c					
In-office bilateral FSO dilation		X						
Endoscopic grading and recording	X	X ^d			X	X	X	X
Sino-Nasal Outcome Test (SNOT-22)		X ^d				X		X
Concomitant medications	X	X	X	X	X	X	X	X
Adverse event reporting	X	X	X	X	X	X	X	X
Urine pregnancy test (female subjects of childbearing potential)	X ^{e,f}	X ^{e,f}						
Documented birth control (female subjects)			X	X	X	X	X	X

Abbreviations: CT, computed tomography; d, days; FSO, frontal sinus ostium/ostia; min, minutes; ml, milliliter.

- ^a. Blood draws to occur at baseline, before balloon dilation procedure and again at Hour 0.5 (±5 min), 1 (±5 min), 2 (±10 min), and 4 (±15 min) after the end of baseline procedure
- ^b. All blood draws should occur in the morning and at approximately the same time of the day during the follow-up visits. Day 1 blood draw to occur 24 hours (±3 hours) after the baseline procedure. Day 3 blood draw to occur 72 hours (±3 hours) after the baseline procedure
- ^c. Urine samples will be collected for a 24-hour duration prior to the baseline visit (pre-procedure) and for a 24-hour duration following the baseline procedure (post-procedure)
- ^d. All endoscopic assessments and SNOT-22 performed prior to the baseline procedure, except for the FSO diameter, which must be performed before and after the balloon dilation procedure.
- ^e. Female subjects with reproductive potential are required to undergo a urine pregnancy test at screening and prior to the baseline procedure.
- ^f. Female subjects are required to confirm their nursing status at screening and baseline

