Prior to the baseline sinus dilation procedure, the FSO will be assessed under endoscopic visualization and the assessment will be recorded on the Endoscopic Scoring Form. Using a 3-mm olive-shaped frontal sinus suction tip, the patency and FSO diameter assessments will be performed. Final subject eligibility will be confirmed based on bilateral stenosis of the FSO on endoscopic assessment. NOTE: Physician may use light-assisted or image-guided instrument such as a smaller diameter frontal sinus seeker tip to confirm access of each FSO and if the sinus is amenable to balloon insertion.

No other devices, spacer, or packing (with or without steroid) may be used during or after the baseline dilation procedure. Aggressive suction and irrigations of the treated site should be avoided, as much as possible.

In subjects in the PK cohort, dilation of the maxillary and/or sphenoid sinus with the same UP Device may be performed, if clinically necessary, after the index dilation procedure. In subjects in the randomized cohort, dilation of the maxillary and/or sphenoid sinus with a commercially available balloon sinuplasty device may be performed, if clinically necessary, prior to randomization. No other surgical procedures at baseline will be allowed.

The steps to be followed for the in-office dilation procedure for this study are as follows:

1. Insert a compatible lightwire through the proximal end of the UP Device.
2. Insert the UP Device into the compatible sinus guide catheter.
 - a. If desired, attach the compatible sinus guide catheter handle to the sinus guide catheter before insertion of the UP Device.
3. Insert the sinus guide catheter into the FSO and position the sinus guide catheter tip opening toward the FSO (See **Section 7.2 Investigational Device** for compatible accessory devices).
4. Confirm that the lightwire is in the sinus, then advance the UP Device through the guide catheter and position it in the targeted FSO. Note: Under endoscopic visualization, ensure that the proximal end of the balloon (yellow single-band marker) is visible outside of the frontal sinus ostium.
5. Inflate the balloon of the UP Device with the compatible inflation device to 12 atmospheres (atm).
6. Hold the inflated balloon at 12 atm for a minimum of ~10 s and maximum of ~30 s.
7. Deflate the balloon.

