8. Reposition the balloon distal to the first inflation site such that the proximal half of the balloon is in contact with sinus mucosa, adjacent to the first inflation site.
9. Repeat steps 5 and 6 to dilate the sinus ostium for a total of 2 inflations in each sinus ostium.
10. Retract the deflated balloon into the guide catheter before removing the dilation system out of the nostril (Note: Do not retract the tip of the UP Device beyond the blue tip marker on the guide catheter to prevent loss of the drug).

PK cohort: Subjects will undergo in-office bilateral sinus dilation with the UP Drug-Coated Device in the frontal sinuses with 2 inflations per sinus (total of 4 inflations per Device).

- Repeat steps 1 through 10 for each FSO with the same UP Drug-Coated Device. Note: Dilation of the maxillary and/or sphenoid sinus with the same UP Device may be performed, if clinically necessary. However, dilation of the maxillary and/or sphenoid sinuses must be performed only after dilation of the frontal sinuses.
- On the day of the baseline procedure, 4 additional blood draws (~ 11 ml at each timepoint) will be performed at 0.5 (\pm 5 min), 1 (\pm 5 min), 2 (\pm 10 min) and 4 (\pm 15 min)

hours following the end of the baseline procedure, defined as removal of UP Device from the nostril after successful dilation of both FSO in each subject.

Randomized cohort: Subjects will undergo an in-office sinus dilation with the UP Drug-Coated Device of the FSO randomized to treatment (2 inflations per device) while the contralateral FSO will serve as control and undergo sinus dilation with a UP Control Device (2 inflations per device).

- Steps 1 through 10 will be followed with each frontal side dilated with the assigned UP Device.

Postoperative care

PK cohort subjects will be required to collect urine samples for 24 hours following the baseline procedure.

After the baseline procedure, subjects in the PK cohort will be allowed and subjects in the randomized cohort will be required to use saline sprays/rinses/irrigations starting Day 2.

PK cohort subjects will not be allowed to use INCS sprays throughout the 30 days follow-up duration. Randomized cohort subjects will be allowed to use INCS sprays starting after the scheduled Day 14 study visit, if medically necessary.

Device disposal

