16.8 Analysis Populations

PK cohort: The PK population will consist of all subjects in the safety population with at least one non-missing and eligible plasma concentration value.

Safety population will consist of all subjects and sinuses exposed to investigational device with successful dilation of at least one FSO.

Randomized cohort: All primary analyses will be conducted on the intent-to-treat population. Additional analyses may be performed on the per-treatment-evaluable population.

- *Intent-to-Treat* (ITT) population will consist of all subjects and sinuses where a sinus dilation was attempted. An attempt occurs when the physician introduces the UP Device into the subject's nostril with the intent of dilation. Subjects and sinuses will be analyzed according to randomization assignment.
- *Per-Treatment-Evaluable* (PTE) population will consist of all randomized patients and sinuses which have received the assigned study device in the target sinus, who have no major procedural protocol deviations, and for whom follow-up data are available.

If a subject decides to discontinue from the study, every attempt will be made to continue to collect the safety and efficacy data according to the protocol procedures.

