7 ANALYSIS COHORTS

7.1 PK Cohort

7.1.1 Safety Population

The safety population will consist of all subjects and sinuses exposed to the investigational device with successful dilation of at least one FSO. All primary and secondary endpoint analyses will be performed on the safety population for the PK cohort.

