9.3.1 PK Cohort

Data from the pharmacokinetic (PK) assessments of plasma MF, plasma cortisol, and 24-hour urinary cortisol concentrations, endoscopic and SNOT-22 scores will be expressed using descriptive statistics, including but not limited to, means, SD, medians, ranges and, where appropriate, coefficient of variation (%). The PK and cortisol parameters, C_{\max} , C_{24} , T_{\max} , and AUC_{0-24} will be calculated by non-compartmental methods according to the definitions below. Nominal sample times will be used in the calculation of all parameters.

C_{\max}	Maximal concentration after the baseline procedure.
T_{\max}	Time at which maximal concentration after the baseline procedure
C_{24}	PK and cortisol concentration 24 hours after the baseline procedure.
AUC_{0-24}	Area under the concentration-time curve from time 0 to 24 hours. The linear/log trapezoidal rule will be used.

Measurement of urinary cortisol excretion for 24 hours prior to the baseline procedure and for 24 hours after the baseline procedure will be analyzed using a validated bioanalytical method with a LLOQ of 1.00 ng/mL.

A_e	The amount of cortisol excreted in urine, will be calculated by multiplying the volume of urine collected over the 24-hour period by the concentration of cortisol measured in the urine sample.
ΔA_e	The change in cortisol urine exposure following administration- calculated as A_e for the 24 hours after baseline procedure minus A_e for the 24 hours prior to the baseline procedure.

The 24-hour urinary cortisol data will be tabulated for each subject for whom amounts are quantifiable.

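### PK and cortisol parameters are computed from nominal times despite a 21–27 h window for the 24 h draw, and PK time zero is undefined when one frontal ostium is not dilated

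*Protocol*

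**What the plan says.** Protocol 11.2 schedules the PK cohort's same-day draws at 0.5, 1, 2 and 4 h after the end of the baseline procedure, "defined as removal of UP Device from the nostril after successful dilation of both FSO in each subject". The numbered steps are repeated for each frontal sinus ostium (FSO), and the last one takes the device out: "Retract the deflated balloon into the guide catheter before removing the dilation system out of the nostril". The same section allows more drug-coated dilation afterwards: "dilation of the maxillary and/or sphenoid sinus with the same UP Device may be performed, if clinically necessary, after the index dilation procedure", with the order fixed as "dilation of the maxillary and/or sphenoid sinuses must be performed only after dilation of the frontal sinuses".

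The schedule in Protocol 6.1 allows ±5 to ±15 minutes on the same-day draws. For the next sample it states: "Day 1 blood draw to occur 24 hours (±3 hours) after the baseline procedure". Follow-up draws are to be taken in the morning.

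SAP 9.3.1 derives Cmax, Tmax, C24 and AUC0–24 for mometasone (MF) and cortisol, with this rule: "Nominal sample times will be used in the calculation of all parameters".

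SAP 7.1.1 defines the PK cohort's safety population as "all subjects and sinuses exposed to the investigational device with successful dilation of at least one FSO". Protocol 16.8 forms the PK population from safety-population subjects with "at least one non-missing and eligible plasma concentration value"; it does not say what makes a value eligible.

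**The concern.** There are two separate timing problems.

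The first is an analysis rule. One sample, the Day 1 draw, supplies C24 and also closes the 4–24 h interval of AUC0–24. If it is drawn at 21 h or 27 h and treated as a 24 h value, both parameters are biased even though the draw complied with the protocol. The morning requirement can push the error in one direction: if a procedure ends at 14:00, a draw before noon the next day comes less than 22 h later.

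The second is the definition of time zero. It requires both FSO to be successfully dilated, but the plan allows for failures. The success rule in Protocol 16.3 and SAP 10.3.1 needs only 80% of attempted FSO, and a subject with one success stays in the safety population. For that subject the same-day draws have no defined starting point. Where maxillary or sphenoid sinuses are dilated after the frontals, the text does not say whether the clock waits for them.

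At stake is the accuracy of the exposure summary in a first-in-human cohort of five, where one or two mistimed profiles carry weight.

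**Working it through.** Neither document states a figure that depends on this point, so there is none to reproduce. The half-lives, absorption rates, late-dose fractions and delays below are assumptions.

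**1. C24 with the Day 1 draw at a window limit.** Late in a first-order decline, C(s)/C(24) = 2^((24 − s)/t½).
- s = 21 h: 2^(3/4) = 1.68 and 2^(3/10) = 1.23, so +68% to +23%.
- s = 27 h: 2^(−3/4) = 0.59 and 2^(−3/10) = 0.81, so −41% to −19%.
- Widening the half-life to 3–12 h gives factors of 2.00 to 1.19 at 21 h and 0.50 to 0.84 at 27 h.

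**2. AUC0–24 at nominal times.** The model is one-compartment, C(t) = [ka/(ka − k)](e^(−kt) − e^(−ka·t)), with ka = 2/h and k = ln 2/t½. Sampling is at 0, 0.5, 1, 2, 4 h and Day 1, using a linear-up/log-down trapezoid. The last interval contributes 20 × (C4 − Cs)/ln(C4/Cs).

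Example, half-life 6 h, arbitrary units:
- C4 = 0.668, C21 = 0.0938, C24 = 0.0663, C27 = 0.0469. The 0–4 h part is 2.804 and the exact AUC0–24 is 8.082.
- Drawn at 24 h: last interval 5.211, total 8.016, error −0.8%.
- Drawn at 21 h: last interval 5.851, total 8.656, error +7.1%.
- Drawn at 27 h: last interval 4.678, total 7.482, error −7.4%.

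| Half-life | C24, drawn 21 h | C24, drawn 27 h | AUC0–24, drawn 21 h | AUC0–24, drawn 27 h |
|---|---|---|---|---|
| 4 h | +68% | −41% | +7.0% | −7.6% |
| 6 h | +41% | −29% | +7.1% | −7.4% |
| 8 h | +30% | −23% | +6.4% | −6.8% |
| 10 h | +23% | −19% | +5.7% | −6.1% |

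A second model took Tmax as 1 h (the sheep value in Protocol 7.3) and half-lives of 3–12 h. Relative to an on-time draw, its AUC0–24 error was +5.5 to +8.0% at 21 h and −5.0 to −6.5% at 27 h.

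These figures are for MF. Cortisol is endogenous and the half-life model does not apply to it, although the nominal-time rule does.

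**3. Subjects without a time zero.** Five subjects treated on both sides give 10 FSO. The rule needs 0.80 × 10 = 8, so two can fail in a cohort still called successful. If they are in different subjects, that is 2 of 5. With independent per-FSO success of 0.90, 0.95 or 0.98 (assumed), the chance of at least one failure is 1 − p^10 = 65%, 40% or 18%.

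**4. Drug delivered after the clock starts.** In the second model, 25–50% of the dose arrives 0.25–0.5 h after time zero.
- At a 0.5 h delay the 0.5 h sample sees only the first part of the dose: 1 − 0.25 = 0.75 or 1 − 0.50 = 0.50 of its correctly timed value.
- Over the whole grid the ratio is 0.50–0.94.
- Tmax moves from 1 h to 2 h in some cases.
- AUC0–24 changes by less than 1%.

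**The case against.** The strongest reply is that little depends on this. The cohort's primary endpoint is successful dilation without an unanticipated serious adverse device effect. Five subjects were chosen to see whether exposure is quantifiable, and the PK reporting is descriptive. That stands, and it limits the weight of the point.

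The large C24 percentages also fall on small values: in the first model C24 is about 2% of Cmax at a 4 h half-life and 22% at 10 h. Nor does that model reproduce the exposure predicted in Protocol 7.4. The ratio AUC/Cmax there is 459/105 = 1376/315 ≈ 4.4 h, against 7.2–13.1 h in the model. The percentages therefore show sensitivity to the window and are not a forecast.

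Two failed FSO is an upper bound. Inclusion criterion k requires access to each FSO to be confirmed, and Protocol 11.1 screens out subjects in whom it cannot be. These checks make a failure less likely but do not supply a time zero when one happens.

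A reader might go further in four ways that the documents do not support:
- That the mistiming cannot be corrected. SAP 9.3.1 says which times enter the calculation, not that actual times go unrecorded. The case report form is not among the documents, and compliance with the draw windows cannot be checked without actual times.
- That every PK summary is distorted. Cmax is an observed maximum, unchanged by the choice of nominal or actual times, and later dilations barely move AUC0–24.
- That the clock does start early. A site could take removal to mean the final removal after all dilations. The reference to an index procedure in Protocol 11.2 favours the literal reading without settling it.
- That the observed values will be formally compared with the predictions in Protocol 7.4. Neither document says so.

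**Conclusion.** The point holds with limited reach. The nominal-time rule in SAP 9.3.1 turns a permitted Day 1 draw at 21 h or 27 h into an MF C24 error of +23 to +68% or −19 to −41%, and an AUC0–24 error of about 6–8%. Those ranges rest on an assumed first-order decline with a half-life of 4–10 h and on draws at the window limits; draws nearer 24 h give smaller errors. The ±3 h allowance also covers Day 3, but only the Day 1 sample enters a SAP parameter.

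The missing time zero after one unsuccessful FSO follows from the text and needs no assumption. A clock that starts before later drug-coated dilations is the literal reading of an ambiguous definition, and it bears mainly on the 0.5 h value and Tmax. The consequences stay within a descriptive summary of five subjects; no hypothesis test and no randomized-cohort result is affected. The correction is cheap and worth making.

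**What to change.** In SAP 9.3.1, compute AUC0–24 and Tmax from actual elapsed times. Report C24 with its actual sampling time and, for MF only, also adjusted log-linearly to 24.0 h. Keep nominal times only for the by-timepoint summary tables.

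In Protocol 11.2, anchor time zero to device removal after the last FSO dilation attempt, successful or not. Record the clock time of every frontal dilation, every additional drug-coated dilation and every draw. Flag subjects who have a later maxillary or sphenoid dilation, and show their 0.5–1 h values and Tmax also relative to the last drug-coated dilation. Moving time zero itself to the last dilation in any sinus is not advised, because frontal absorption would then fall before time zero and outside AUC0–24. These changes concern only the sampling clock and leave the procedure as it is.

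The cost is a few sentences, clock-time fields on the case report form and some programming, with no extra draws or visits. The PK cohort enrolls first, so the protocol change may come late for some subjects; the SAP change still helps wherever clock times were recorded.

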11.3 Follow-Up Phase

The follow-up period begins immediately post-procedure (once the subject exits the clinic).

PK cohort

Each subject will return for up to 6 follow-up visits (see **Section 5 Study Flow Diagram** and **Section 6 Schedule of Assessments**).

- Day 1 (24 hours \pm 3 hours after the baseline procedure)

- Day 3 (72 hours \pm 3 hours after the baseline procedure)
- Day 7 \pm 2 days
- Day 14 \pm 2 days
- Day 21 \pm 2 days
- Day 30 \pm 3 days

The protocol-required follow-up assessments through Day 30 will consist of:

- SNOT-22 questionnaire (at Days 14 and 30)
- Endoscopic examination, grading and video recording (at Days 7, 14, 21 and 30)
- Blood sample collection of 11 ml (at Days 1, 3, 7, 14, and 30)
 - All blood draws must occur in the morning and at approximately the same time of the day during the follow-up visits.

Randomized cohort

Each subject will return for up to 5 follow-up visits for endoscopic grading and video recording (see **Section 5 Study Flow Diagram** and **Section 6 Schedule of Assessments**).

- Day 7 \pm 2 days
- Day 14 \pm 2 days
- Day 21 \pm 2 days
- Day 30 \pm 2 days
- Day 60 \pm 7 days

Unscheduled visits

Subjects may come in for additional unscheduled office visits if necessary. Circumstances that may warrant additional visits include but are not limited to:

- Worsening of sinus symptoms, and/or
- Sinus-related adverse events requiring medical evaluation.

The assessment at an unscheduled visit will consist of:

- SNOT-22 questionnaire (PK cohort only), and,
- Endoscopic examination, grading and video recording.

12 CONCOMITANT MEDICATION

The study standardized medication regimen will be as follows:

- Leading up to the baseline procedure, there is a 30-day restriction for use of parenteral and injected steroids (e.g., Kenalog).

- Leading up to the baseline procedure, a 14-day restriction for use of oral steroids, budesonide or other sinus steroid irrigations/rinses or drops, and nebulized steroids administered nasally.
- After the baseline procedure, subjects will be allowed in the PK cohort and required in the randomized cohort to use saline sprays/rinses/irrigations starting at Day 2.
- If infection is suspected at any time during the study, treatment with antibiotics will be permitted.
- Use of intranasal corticosteroid (INCS) sprays is allowed starting after Day 14 visit in the randomized cohort, if clinically necessary, and not allowed throughout the 30-day follow-up period in the PK cohort.
- Use of other corticosteroids (e.g., oral, parenteral, injections, budesonide or other sinus steroid irrigations/rinses or drops, breath powered steroid delivery [e.g. XHANCE™, fluticasone propionate] nebulized steroids administered nasally) will not be permitted during the study follow-up unless clinically necessary (see **Section 13 Medical and Surgical Interventions**).
- If already on such medications, use of orally-inhaled steroids for control of asthma will be permitted.
- Use of corticosteroid-eluting sinus implants (PROPEL®, PROPEL® Mini, PROPEL® Contour, SINUVA®) or other nasal packing and spacers is prohibited 14 days prior to baseline, during the baseline procedure and through Day 30 in the PK cohort and through Day 60 in the randomized cohort.
- To the extent possible, subjects will be maintained on stable regimens of leukotriene inhibitors and/or immunotherapy (e.g., Montelukast, Zafirlukast, Zileuton) for allergies throughout the follow-up duration, if currently on such regimens.

All sinus-related medications will be recorded in the EDC system including their full brand/trade or generic names (whichever prescribed), dose, frequency, indication, start and end dates are coded using the World Health Organization drug dictionary.

13 MEDICAL AND SURGICAL INTERVENTIONS

Subsections below describe the rescue treatments consisting of medical and surgical interventions that will be allowed during the study follow-up based upon subject's symptomatic and endoscopic outcomes.

13.1 Medical Intervention

During study follow-up, INCS sprays will be allowed starting after Day 14 visit, if clinically necessary, for subjects in the randomized cohort and not allowed throughout the 30-day follow-up period for subjects in the PK cohort.

Other corticosteroids (e.g., oral, parenteral, injection, budesonide or other sinus steroid irrigations, rinses or drops, nebulized steroids administered nasally) will not be permitted unless

there is a clinically significant increase or persistence in frontal sinus inflammation occurs, coupled with subject complaint of sinusitis symptoms that cause subject to request medical intervention.

13.2 Surgical Intervention

Surgical intervention (e.g., repeat balloon dilation or sinus surgery, in-office polypectomy) may be required in cases where a clinically significant increase or persistence in frontal sinus inflammation occurs, coupled with complaints of sinusitis symptoms that cause subject to prefer a surgical intervention (e.g. sinus surgery).

All oral steroid and surgical intervention will be noted on the concomitant medication and follow up CRFs (see **Section 16.6 Handling Steroid or Surgical Interventions**).

